### **Participant Randomization for Aim 2**

After screening and consent, participants will be randomized to one of three groups (IG, EG or the behavioral control (BC, Education)). Participants will not be blinded to treatment group, but the instructors of the interventions will be blinded to performance on all outcome measures, and raters of all functional performance measures will be blinded to treatment group. The PI will train raters, qualified research assistants, in proper administration of all measures.

#### Specific Aim 2: Experimental Plan

IG: Internally guided

EG: Externally guided

BC: Behavioral control: health education

Outcome measures: Mobility, cognition, scans of IG and EG foot tapping

### **Intervention: IG and EG training in adapted tango classes for participants with PD**

**Dosage:** Participants shall receive 1.5 hours of progressive IG or EG adapted tango dance, or BC, a health education class 2 days/week for 12 weeks, with a goal of 20 completed lessons, in the Atlanta

VA Rehabilitation R&D Center's 41 ft x 34 ft Movement Studies Lab. To examine neural circuitry in conjunction with intervention, an effective dose of that intervention must be used, i.e., one with demonstrated improvements in mobility and balance via outcome measures of interest. Twenty sessions were used previously and were effective at improving mobility (See preliminary studies). We expect 20 lessons over 12 weeks will provide enough therapy for both functional improvements to manifest as well as neurological changes to have occurred, because one month after training cessation, observations revealed maintained gains in the absence of treatment. Thus, all participants must complete all 20 lessons to include their data in analyses. Participants will have ample opportunity to complete 20 lessons: there will be 4 lessons offered per week for 12 weeks (48 total sessions). If necessary, make up sessions will be offered. To date, we have experienced ~15 % attrition. Notably, in a recent pilot study in Atlanta examining intensive tango, there was 0% attrition.

**Adapted tango:** Composed of simple steps, tango involves frequent movement initiation and cessation, multi-directional perturbations and varied rhythms. Participants focus on trunk control and stepping strategies, coordination, somatosensory awareness, attention to partner, path of movement, and aesthetics. Sessions will begin with a typical dance class warm-up consisting of breathing, limbering and postural alignment to upbeat music. Novel step elements will be introduced every class period. Those with PD will partner with an individual without PD. After novel step introduction, the instructor will present rhythmic training, which is indispensable to partnered dancing. Participants will learn 'typical' rhythms from tango and Latin dances, based upon the system of quicks (Q) and slows (S), ubiquitously used in ballroom dance training to understand the temporal relationship of movement to music. Two quick beats equal one slow beat. Accompanying new rhythms to simple moves first allows transfer of the rhythm to more complex steps. Thus, the instructor will physically introduce rhythms by having participants clap, then tap a foot, then march in place and then walk to the rhythm.

In the last third of class, the new step of the day will be reviewed and added on to previously learned steps. We will maintain manageable class sizes (e.g., no more than 10 pairs of participants with PD and partners) to maximize safety. Participants will dance with new partners (without PD) every 10 minutes, a widely practiced method designed to enhance learning in partnered dance lessons. Steps will be performed in an adaptation of the traditional ballroom frame, holding each other's bent elbows, maintaining forearms parallel to the floor. During the 20 classes, participants will be randomized to either IG or EG roles, i.e., to leading or to following. Leaders (randomized to IG group) will always dance as leaders, and followers (randomized to EG group) as followers.

Those in IG training will choose direction, timing and amplitude of each successive step. Those in EG will learn to attend to sensory cues for movement direction, timing and amplitude of steps, communicated from their partner to them via the frame and center of mass. Choreographic biomechanical patterns will be very similar between IG and EG training. The only difference between leading and following will be whether or not external guidance of movement is provided, after steps are learned.

The instructor and healthy assistants, trained in spotting techniques, shall carefully monitor all participants' safety. Participants will be encouraged to take regular breaks. Spouses, friends and caregivers will serve as dance partners. Also with methods used several times previously by the PI, student volunteers recruited from surrounding colleges and universities will serve as assistants and dance partners. The PI will educate student volunteers about PD- and aging-related posture and gait problems, proper assistance techniques to use for balance loss and methods for monitoring balance and anticipating falls.

**Behavioral Control (BC) Condition:** Participants will attend group health education sessions as per Wolf et al., (1996) adapted to the needs and interests of individuals with PD. They will engage in *IRB 60613 Motor Training in PD*

Study Version 6/14/16

interactive small group, large group and partnered learning. Discussion will be greatly encouraged. Emory medical students as well as experts from Emory School of Medicine and other local universities or organizations will present information. Student volunteers will participate in these sessions by moderating the lectures, assisting with the presentation of information and leading discussions. Participants in this training will be instructed not to change their habitual exercise routines. After completing health education, participants may be assigned to an IG or EG training class but will not undergo evaluations.

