### **2. Abstract:**

Persons with Parkinson's disease (PD) have impaired mobility, which adversely affects their quality of life. The effectiveness of adapted tango dance, in which participants both lead (internally guide: IG) and follow (externally guide: EG) movement has been demonstrated (Hackney & Earhart 2009, 2010). To improve outcomes in those with PD, the underlying neural mechanisms for both motor impairments and improvement must be investigated. IG and EG movements have distinct neural patterns. Individuals with PD have trouble with IG movement but this problem is helped by strategies employed while "leading". During "following", participants with PD can exploit multiple external cues, which facilitate movement in PD, because EG tasks bypass the basal ganglia (Freedland et al., 2002).

Using a randomized controlled trial design, we will begin with an functional Magnetic Resonance Imaging (fMRI) investigation. We will examine neural correlates of a clinically-used foot-tapping task, during IG and EG conditions in older persons with and without PD. Then, we will assess the relative effectiveness of IG versus EG training used in an adapted tango class, compared to a behavioral control (health education) for improved mobility and foot tapping. Participants with PD will be assessed for disease severity, and will receive tests of outcome measures while "OFF" and "ON" medications, 1 week before training, and 1 week and 1 month after training. Participants must attend 20 lessons of IG or EG adapted tango in 12 weeks, taught by an experienced instructor. In an fMRI scanner, we will assess participants for improved foot tapping after training and investigate changes in activation in specific neural circuits in conjunction with training effects upon mobility.

Our long-term goal is to optimize motor training for persons with PD by understanding lower limb motor circuitry in PD as well as neural changes in circuitry through which training is effective.

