## **5. Study design and Methods**

**Overview:** To accomplish Aim 1, we will use functional Magnetic Resonance Imaging (fMRI) to determine neural circuitry underlying IG and EG foot-tapping in 24 veterans with and 24 veterans without idiopathic, mild-moderate PD (Hoehn & Yahr stages II-III). To accomplish Aim 2, we propose a randomized controlled trial to evaluate the relative effectiveness of IG and EG movement to improve mobility in veterans with PD. We will also measure corresponding changes in neural activation during IG and EG foot-tapping, as a result of intervention. Participants will be randomized

to receive EG, IG or behavioral control (BC; health education) training over 12 weeks. Participants will be tested on all outcome measures while “OFF” and “ON” medications at a standardized time of day. We are observing participants in outcome measures while OFF medications in order to avoid dyskinesia, and medication fluctuations that may impact functional activity of networks of interest. Participants will complete outcome measure testing for mobility, QOL, executive function, procedural learning, spatial cognition, and foot-tapping 1 week before training (pre), and 1 week (post) and one month (follow-up) after completing all training. Using fMRI we will also investigate the relationship of changes in neural activation in the participants before and immediately after training.

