**Hypothesis 1:** Power calculations for Aim 2 are based upon an assumed 4-point improvement and effect sizes  $> 0.8$  on the BBS after 12 weeks of adapted tango, which was attained previously (see Preliminary Studies), and the minimal detectable change on the BBS in parkinsonism is 2.84 points. Therefore, with a total sample size of 63 participants (21 participants in each of 3 groups: IG, EG, and BC) a repeated measures (RM) ANOVA with 3 levels of repeat will be sensitive to between-within interaction main effect size of  $f(v) = 0.44$  ( $F_{4,114} = 2.45$ ) with a power of 0.80 at  $\alpha=.05$ . Post hoc sensitivity to effects between groups will be  $d = 0.90$ , and within groups,  $d_z = 0.65$ . To reflect an anticipated 20% attrition, we will recruit an additional 4 participants per group. Thus we will recruit 25 participants per group, for a total of 75 individuals with PD recruited for Aim 2. **Hypothesis 2:** 25 participants per group will be sufficient to detect effects for the imaging (activation and resting state) components of Aim 2 as well, based on studies conducted to determine reasonable sample sizes for fMRI studies, that demonstrate at least 20 participants in each group are necessary. **Hypothesis 3:** Differences in RSfc have been noted between different groups of individuals with PD in sample sizes of 16 per group; therefore, with 25 individuals per group, we will be able to detect differences between groups.

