## Statistical Analysis Plan for Aim 2, Hypothesis 1, 2 and 3:

- **Participant demographics:** Descriptive statistics will characterize groups. One-way ANOVA will determine differences, if any, between groups on baseline measures.
- **Behavioral Outcome measures:** A 3 group (IG, EG, BC) x 3 time (pre, post test, follow-up (1-month later)) RM ANOVA will be used to detect main effects. Appropriate post hoc tests will be used to determine within- and between-group differences,  $p<0.05$ , for **BBS, the primary outcome** measure upon which Aim 2 is powered. Statistical tests run on all secondary variables will be corrected for multiple comparisons.
- **Brain Activation Analyses for Aim 2, Hypothesis 2:** Similar to Aim 1 procedures, average percent signal change for IG and EG tasks (relative to baseline) for each participant will be extracted from the centers of gravity of the activated regions and submitted to hierarchical regression analyses to determine whether they correlate with behavioral measures (foot-tapping absolute timing errors and average amplitude). Disease severity and PD duration will be covariates. To determine the effects of time and training status we will submit the percent signal change to a 3 group (IG, EG and BC) X 2 time (pre, post) RM ANOVA. Post-hoc analyses will be corrected for multiple comparisons. The **primary outcome** will be t-contrast maps and effect size maps from ANOVA, which will be evaluated for changes in STC and CTC circuits.

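### The primary Berg Balance Scale comparison (Aim 2, Hypothesis 1) is restricted to participants who complete all 20 lessons, and no as-randomised analysis is named

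*Combined protocol and SAP*

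**What the plan says.** All places are in the combined protocol and SAP.

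- **Section 5, Intervention, Dosage:** "Thus, all participants must complete all 20 lessons to include their data in analyses". The reasoning just before this sentence names functional as well as neurological change, and the sentence is not limited to imaging. It therefore covers BBS and all three arms: internally guided (IG), externally guided (EG) and behavioral control (BC).
- **Section 7, Statistical Analysis Plan for Aim 2, bullet on behavioral outcomes:** the model is given as "A 3 group (IG, EG, BC) x 3 time (pre, post test, follow-up (1-month later)) RM ANOVA will be used to detect main effects". BBS is the primary outcome. No analysis population and no rule for missing BBS data is given.
- **Section 7, Power Analyses for Aim 2, Hypothesis 1:** the powered test is the interaction, at f(V) = 0.44. The plan words it this way: "a repeated measures (RM) ANOVA with 3 levels of repeat will be sensitive to between-within interaction main effect size of". The calculation uses 63 participants (21 per group). On losses: "To reflect an anticipated 20% attrition, we will recruit an additional 4 participants per group". That gives 25 per group and 75 in total.
- **Section 5, Overview:** visits are timed "1 week before training (pre), and 1 week (post) and one month (follow-up) after completing all training". How this applies to someone who does not complete is not stated.

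No section names an as-randomised analysis or a sensitivity analysis in all randomised participants. The only missing-data statement concerns discarded fMRI volumes.

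**The concern.** Hypothesis 1 asks which training improves mobility more, relative to the other training and to a behavioral control. Randomisation makes the arms comparable at entry. Completing 20 lessons is decided afterwards and may depend on how a participant is doing. If it does, and if the dependence or the completion rate differs between arms, the completers-only contrast mixes the training effect with who completed. Recruiting four extra per group restores numbers, not comparability. Because the plan names no analysis in everyone randomised, a reader of the results could not check whether selection had occurred. If non-completers are not evaluated, the data for such a check cannot be recovered later.

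**Working it through.** **1. The plan's own power figure.** For the group x time interaction with 3 groups and 3 visits, df1 = 4, df2 = (63 − 3) x 2 = 120 and noncentrality = 0.44² x 63. Power is 0.792 against the stated 0.80, so it reproduces. By these figures 75 − 63 = 12 participants (16%) are recruited but not in the powered sample, which fits an analysis of those who remain.

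**2. When the rule biases the interaction test.** The test concerns change over visits. Completion related only to a stable BBS level cancels out. Bias needs completion to be related to BBS *change*, and that selection to differ by arm, either in the fraction excluded or in the strength of the relation.

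**3. Illustration of size.**
- *Inputs:* 25 randomised per group (Power Analyses for Aim 2). Assumed, not in the documents: correlation ρ = 0.2 to 0.5 between completion and BBS change, and excluded fractions q.
- *Formula:* with a normal selection variable, the shift in an arm's mean change, in SDs of change, is ρ·φ(z_q)/(1 − q). The factor φ(z_q)/(1 − q) is 0.350 at q = 0.20, 0.195 at q = 0.10 and 0 at q = 0.
- *False-positive rates:* pairwise by noncentral t (two-sided 0.05). The interaction test by simulation (60,000 runs, compound symmetry, between-visit correlation 0.7, no true effect, both tango arms 20% excluded).

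| Excluded, tango vs BC | Spurious d | Pairwise | Interaction test |
|---|---|---|---|
| 20% vs 10% | 0.155 x 0.2 = 0.03 to 0.155 x 0.5 = 0.08 | 5.1–5.7% | 5.1–5.4% |
| 20% vs 0% | 0.350 x 0.2 = 0.07 to 0.350 x 0.5 = 0.175 | 5.6–8.8% | 5.2–7.4% |
| 20% vs 20%, equal selection | 0 | about 5% | about 5% |
| 20% vs 20%, selection in tango arms only | 0.07–0.175 | not computed | 5.2–7.2% |

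IG and EG are treated alike in every row, so the IG versus EG contrast is unbiased in these scenarios. It would be biased only if selection differed between those two arms.

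**4. Power if non-completers are included.** Assume 20% non-completion (5 of 25 per group), d = 0.90 in completers (the plan's post hoc sensitivity), and non-completers who gain a share g of the effect. Then d = 0.90 x (20 + 5g)/25:
- g = 0: d = 0.72, power 0.70
- g = 0.5: d = 0.81, power 0.80
- g = 1: d = 0.90, power 0.88

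Completers only, at d = 0.90: power 0.79 with 20 per group and 0.81 with 21.

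**5. How much bias inclusion removes.** Take the 20% versus 0%, ρ = 0.5 case, with a model that conditions on the pre score (between-visit correlation 0.7). The 0.175 SD falls to about 0.14 if no non-completers return, 0.06 if half return and 0 if all return.

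**The case against.** **Twenty lessons is described as a goal.** It is, in the same paragraph, but as an attendance target. The later sentence expressly governs whose data are analysed.

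**Few will be excluded.** With 48 sessions on offer, make-up sessions, and past attrition of about 15% and, in one pilot, 0%, exclusions may be rare. This stands as a reason to expect a small effect. It does not change who is analysed.

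**Attrition is not completion.** This stands. A reader might take the anticipated 20% attrition as the fraction the rule removes. The documents do not support that. Dropouts who never return are lost under any rule; the rule adds only people who could be evaluated but fell short of 20 lessons. That increment is unknown and may be close to zero.

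**A mechanistic study needs full exposure.** This is fair for imaging Hypotheses 2 and 3, which are outside this point. Hypothesis 1 is posed as a randomised comparison of relative effectiveness.

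**The arms visibly differ.** A reader might infer that completion must differ by arm, because "Participants will not be blinded to treatment group" and, for the control arm, "After completing health education, participants may be assigned to an IG or EG training class but will not undergo evaluations". These facts make a difference conceivable. They show neither that one exists nor its direction.

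**The visit wording conflicts.** A reader might set the Abstract, "1 week before training, and 1 week and 1 month after training", against the Section 5 Overview. The Abstract is only a shorter paraphrase, and the two Exit Questionnaire entries in Section 5 also count from completion of training. What remains is silence about non-completers.

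**Conclusion.** The point holds on the text. A post-randomisation condition decides who enters the primary BBS comparison, and no as-randomised analysis stands beside it. It should be fixed.

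The size and direction of any bias cannot be derived: there is no completion by arm, no stated relation between completion and BBS change, and no BBS standard deviation. Under the assumptions above the planned interaction test would have a false-positive rate of at most 7.4%, against a nominal 5%, and most scenarios lie close to nominal. The documents do not support a claim that the tango-versus-control result will be inflated, or that IG versus EG is distorted.

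**What to change.** 1. **Section 5, Dosage.** Replace the sentence with: *The primary BBS analysis (Aim 2, Hypothesis 1) includes all randomised participants with BBS data in their assigned group, regardless of lessons completed. Participants who completed 20 lessons form a labelled secondary BBS set, which is also the set used to relate BBS to imaging in Hypotheses 2 and 3.* The last clause matters because Hypothesis 2 builds on the mobility result of Hypothesis 1.
2. **Section 7, Behavioral Outcome measures.** State the same set and use all available visits, for example with a likelihood-based mixed model (group, time, group x time) in place of the RM ANOVA.
3. **Visits.** State that non-completers are invited to the planned post and 1-month BBS evaluations. Reconcile the wording that counts from completion of training (Section 5 Overview and both Exit Questionnaire entries) so that it also covers them. The sponsor sets the timing.
4. **Reporting.** Give non-completion and non-return by arm.

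**Cost.** Besides the wording, up to about 30 BBS visits if 20% do not complete (3 x 5 = 15 participants x 2 visits). Dilution is possible: pairwise power is lower than with completers only if non-completers gain nothing, about equal if they gain half, and higher if they gain the full effect and all return. Bias from non-completers who do not return is reduced only in part. No change to lesson number or class content is proposed.

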#### **Participation**

- **Impact on participation and autonomy scale**- This is a self-report measure and includes multiple domains of participation along with a strong focus on an individual's autonomy in his/her choices for daily activity participation.
- **Physical Activity Scale for the Elderly**- This scale is an easily administered and scored research instrument that measures the level of physical activity in individuals aged 65 years or older.

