### **Plans to minimize adverse physical sequelae during the intervention:**

The following procedure, which was previously successful with other dance interventions for people with PD and oldest-old adults with low vision will be employed to minimize risk of falls and ensuing physical sequelae:

During classes participants will be continually monitored by the teacher trainee and trained assistants for fatigue and instability. The trained assistants will be instructed that their primary purpose is to prevent falls or other adverse events. Furthermore, to avoid accident outside of the class time, participants will be instructed not to practice the dance steps they learn at home or elsewhere outside of the class. Participants will be instructed to practice dance steps only when supervised by the instructor and assistants. Participants will be asked about their fall history at each observation, monthly during the intervention and all events will be documented.

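### The visible protocol asks only the control arm to hold outside exercise constant, so other exercise could bias the tango-versus-control comparison in either direction.

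*Combined protocol and SAP*

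**What the plan says.** The BC condition is described in section 5, at the end of the text on the intervention. Of health-education participants it says: "Participants in this training will be instructed not to change their habitual exercise routines".

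The dosage and adapted tango paragraphs in the same section contain no such request for the IG and EG arms. The nearest rule is among the fall-safety measures (Plans to minimize adverse physical sequelae during the intervention): "participants will be instructed not to practice the dance steps they learn at home or elsewhere outside of the class". It concerns dance steps and does not mention walking, gym work, physiotherapy or any other activity.

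Three other statements bear on the point.

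- Blinding (Participant Randomization for Aim 2): "Participants will not be blinded to treatment group". Raters of functional performance are blinded.
- The two tango arms (adapted tango description): "The only difference between leading and following will be whether or not external guidance of movement is provided, after steps are learned".
- Activity measurement (Participation, and Table 2): PASE is in the outcome battery. It is described as an instrument that "measures the level of physical activity in individuals aged 65 years or older".

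The analysis plan for Aim 2, Hypothesis 1 says that a 3 group by 3 time "RM ANOVA will be used to detect main effects", with BBS as primary outcome. It names no activity covariate and no check on outside exercise.

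**The concern.** The comparison with BC is meant to show what the training does. For that, other influences on balance should be handled alike in the arms compared. Exercise is such an influence on the protocol's own account: the introduction lists several movement programs as effective in Parkinson's disease, and the Significance section says group exercise rehabilitates motor impairment.

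As written, one arm is asked to hold this influence constant and the two arms compared with it are not. All participants know which arm they are in. If outside exercise then changes differently in the tango arms and in BC, part of the BBS difference belongs to that exercise and not to the training. Blinded rating does not help, because the balance scores would really differ. Randomisation does not help either, because the divergence would arise after it.

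**Working it through.** **1. The instructions side by side, as far as the visible text goes**

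| Arm | Told about outside exercise | Told about dance practice outside class |
|---|---|---|
| BC | Keep the habitual routine | Not taught dance during the evaluated period |
| IG | Nothing stated | Not to practise |
| EG | Nothing stated | Not to practise |

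IG and EG have the same entries, so their comparison carries no imbalance from this source. IG versus BC and EG versus BC do.

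**2. Form of the bias**

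Let *b* be the change in BBS due to outside exercise in a tango arm minus that in BC. The expected observed difference is the training effect plus *b*. If tango participants take up other exercise, *b* is positive. If two 1.5-hour classes a week displace exercise they used to do, *b* is negative. The documents give neither the frequency of either behaviour nor its effect in BBS points, so *b* has no value that can be derived.

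**3. What a given *b* would do (illustration only)**

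Inputs from Power Analyses for Aim 2: 21 participants per group, alpha 0.05, an assumed 4-point improvement and an effect size above 0.8. If that effect size is the 4 points divided by an SD, the SD is below 4/0.8 = 5 points.

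Assumptions that are not in the documents: a two-sided two-sample t-test, SD of 4, 5 or 6, and the values of *b*.

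Formula: noncentral t with 2 × 21 − 2 = 40 degrees of freedom and noncentrality (difference/SD) × √(21/2).

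Check against the plan: its stated between-group sensitivity of d = 0.90 gives power 0.81 by this formula, in line with the intended 0.80.

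Chance of a significant tango-versus-BC difference when training has no effect (5% if *b* = 0). The same figures apply with either sign; a negative *b* would favour BC.

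| Size of *b* (BBS points) | SD 4 | SD 5 | SD 6 |
|---|---|---|---|
| 0.5 | 6.8% | 6.2% | 5.8% |
| 1 | 12.4% | 9.7% | 8.2% |
| 2 | 35.3% | 24.4% | 18.4% |

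Power at SD 5 if the true tango-minus-BC difference were 4 points (a further assumption: the plan states 4 points as an improvement after tango, not as a difference from BC):

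| *b* | Expected observed difference | Difference/SD | Power |
|---|---|---|---|
| −0.5 | 3.5 | 0.7 | 0.60 |
| 0 | 4.0 | 0.8 | 0.72 |
| +0.5 | 4.5 | 0.9 | 0.81 |

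A half-point shift does little to the false-positive rate but moves power by about 0.10 to 0.12. Shifts of 1 to 2 points would matter more. Nothing in the documents says which row applies.

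**4. Whether the plan would notice**

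PASE is in the battery, and outcome measures are taken at pre, post and follow-up. A broad reading of the behavioural analysis could include PASE as a secondary variable. It is not named in the Aim 2 list of secondary motor measures or in the analysis plan, and no text uses it to check outside exercise.

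**The case against.** The best case for the plan has four parts.

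- **The instruction has a purpose in BC.** People who know they were not given dance, and who attend health education, may be prompted to start exercising. Asking them not to protects the control condition. This stands as a reason to instruct BC. It is no reason to leave the tango arms without the instruction.
- **The most obvious route is closed.** Practising dance outside class is barred. This stands, and it narrows the exposure to other exercise. The documents give no reason to expect tango participants to take that up.
- **The text is incomplete.** Consent pages are not available, and the informed consent section says study procedures are explained in detail at recruitment. A general instruction to all arms may exist there. This stands: the finding is limited to the visible protocol.
- **Activity is already measured.** PASE by arm and visit may be analysed anyway. This stands in part, since no text assigns PASE that use.

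A reader might infer that the bias must favour tango, because only the tango arms are free to exercise more. The documents do not support that. The absence of an instruction permits change both ways, and class attendance could displace other exercise. A reader might also want to express the bias as a percentage of the 4-point figure. That would need uptake and benefit rates that the documents do not give, and it would set a between-arm bias against a gain described as improvement after tango.

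**Conclusion.** The point holds as a minor weakness of design that is cheap to remove. In the visible protocol, a co-intervention that the protocol considers active is held constant by instruction in one unblinded arm and not in the two arms compared with it. The tango-versus-BC difference on BBS could be biased upwards or downwards. The size is unknown, and the tables above show only what assumed shifts would do. IG versus EG is not affected.

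The conclusion rests on two things: that no common instruction is given in documents not available here, and that outside exercise affects BBS, as the protocol's own background implies. It does not show that outside exercise will diverge.

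**What to change.** Give all three arms the same instruction about exercise outside the study, at enrolment and in the same words. If a common instruction already exists in the consent material, repeat it in the protocol. If the difference between arms is intended, state the reason.

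As a supporting check, prespecify a table of PASE by arm at pre, post and follow-up, with two cautions beside it. The scale is described for people aged 65 or older, whereas recruitment targets ages 40 to 85. Nothing in the protocol says that it separates study classes from other activity, so attendance may raise the score in the tango arms. A higher tango score would therefore not by itself show more outside exercise.

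The cost is one sentence in the participant instructions and one table from data already planned. Sample size, power and the primary analysis stay as they are. If enrolment has already begun, the table can still be added.

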### **Outcome Measures of Functional Performance (Aim2, Hypothesis 1):**

Measures of motor function, PD QOL and explanatory measures of executive function, procedural learning, and spatial cognition will be conducted at evaluations (pre, post and 1 month follow-up). All evaluations will be performed in the safety-monitored Movement Analysis Laboratory at the Atlanta VAMC. All outcome measures will be directly measured with an instrument or self completed by the participant, except for BBS and other scales judged by a trained rater, which will be videotaped for a blinded and qualified rater (e.g., trained physical therapy students or research assistants) not involved with the project otherwise.

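### Nothing makes the health-education controls' optional tango class wait for their 1-month follow-up, so the control value at the third time point of the primary analysis can follow tango exposure

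*Combined protocol and SAP*

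**What the plan says.** The rule on later tango for controls is one sentence in section 5, under Behavioral Control (BC) Condition: "After completing health education, participants may be assigned to an IG or EG training class but will not undergo evaluations". It names completion of education as the trigger and gives no start date. The same paragraph asks controls to keep their usual exercise habits, but it addresses people in the education programme and is not tied to the follow-up visit.

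The Overview of section 5 schedules outcome testing "1 week before training (pre), and 1 week (post) and one month (follow-up) after completing all training". The section on outcome measures for Aim 2, Hypothesis 1 repeats that these measures "will be conducted at evaluations (pre, post and 1 month follow-up").

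Section 7 names the BBS as the primary outcome for Aim 2 and analyses it with "A 3 group (IG, EG, BC) x 3 time (pre, post test, follow-up (1-month later)) RM ANOVA". The power analysis for Aim 2 likewise assumes three repeats in three groups of 21. BC at follow-up is therefore one of the nine cells of the primary analysis.

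**The concern.** Education ends about one month before the BC follow-up visit, and the crossover sentence opens the tango classes at the start of that month. Read as written, it allows a control to attend several weeks of IG or EG training and then give the follow-up BBS that stands for no tango.

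The follow-up contrast carries weight. Section 5 (Dosage) justifies the 20-lesson programme by gains still present one month after training stopped. To show that against control, the trial needs controls who have not begun tango. If tango works as the plan assumes, controls who have started will have moved toward the tango arms. Retained gains in IG and EG would then look like a fading difference from control.

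**Working it through.** **1. The plan's own figure.** Section 7 states power 0.80 for the group-by-time interaction at f(V) = 0.44, N = 63, alpha 0.05. With a noncentral F, df1 = 4, df2 = (63 − 3) × 2 = 120 and λ = N f² = 63 × 0.44² = 12.20, power is 0.792. For the post hoc between-group effect d = 0.90 with 21 per group, two-sided 0.05 (sidedness assumed), the noncentral t has df = 40 and ncp = 0.90 / √(2/21) = 2.92, giving power 0.812. Both agree with 0.80.

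**2. Tango exposure before follow-up.** Section 5 plans 2 classes a week toward 20 lessons. About 4 weeks separate the end of education from follow-up, so an immediate start gives 2 × 4 = 8 lessons, or 8/20 = 40% of the programme. A start after the 1-week visit leaves about 3 weeks: 6 lessons, 30%.

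**3. Assumptions not in the documents.** Gain is proportional to lessons, education does not change the BBS, and a share s of controls starts at once. The extra spread from mixing crossed and uncrossed controls is ignored.

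**4. Pairwise contrast at follow-up.** d(s) = 0.90 × (1 − 0.4s); difference = 4 × (1 − 0.4s) points, from the plan's assumed 4-point gain; 21 per group.

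| Share crossing over | Difference (points) | d | Power |
|---|---|---|---|
| 0% | 4.0 | 0.90 | 0.81 |
| 25% | 3.6 | 0.81 | 0.73 |
| 50% | 3.2 | 0.72 | 0.62 |
| 100% | 2.4 | 0.54 | 0.40 |

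If all controls cross over but take only 6 lessons, d = 0.90 × 0.7 = 0.63 and power is 0.51.

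**5. Group-by-time interaction.** Means (pre, post, follow-up): IG and EG 0, 4, 4; BC 0, 0, g, with g = 0 (no crossover) or 0.4 × 4 = 1.6 (full crossover). There are 20 per arm (25 recruited less the plan's 20% attrition). SD 5 is assumed; it is what 4 points at an effect size of 0.8 implies (4/0.8). The within-person correlation r is assumed equal for all pairs of visits. λ = n × Σ(interaction effects²) / [SD² (1 − r)], df 4 and 114. The sum of squares is 7.11 for g = 0 and 5.40 for g = 1.6. At r = 0.5, λ = 20 × 7.11 / 12.5 = 11.38 falls to 20 × 5.40 / 12.5 = 8.65.

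| r | Power, no crossover | Power, full crossover |
|---|---|---|
| 0.3 | 0.592 | 0.465 |
| 0.5 | 0.759 | 0.623 |
| 0.7 | 0.945 | 0.862 |
| 0.8 | 0.994 | 0.970 |

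At r = 0.5, partial crossover (g = 0.4 or 0.8) gives 0.71 at 25% and 0.67 at 50%.

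**6. What is not touched.** IG versus EG does not involve the controls. The activation and connectivity analyses in section 7 use pre and post only. The pre-to-post BBS contrast with control stands if the 1-week visit precedes any class; the text does not fix that order either.

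**The case against.** The sentence permits crossover and does not schedule it. The Overview counts follow-up from the end of all training, and controls are told to keep their exercise habits. Both lean toward an untreated follow-up, and staff may well intend to wait. That stands: this is a missing rule, and no passage places tango before follow-up. Neither hint sets an order, though, and the one explicit condition is met a month too early.

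The full-crossover figures are also a worst case. They need every control to start at once and attend fully, and the SD and r are assumed. This stands too, and at high r the interaction loses little power. The results therefore have to be read as a range.

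A reader might go further and infer that controls who join a class lose their follow-up visit, because the sentence says they are not evaluated, and that a conventional RM ANOVA would then drop them altogether. The documents do not support this. The natural meaning is that the later class is not itself evaluated. Cancelling the visit would contradict the three-visit schedule and the analysis that names BC at all three times.

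**Conclusion.** The gap is real and should be closed. As written, the plan allows the BC follow-up BBS in the primary 3 × 3 analysis to be measured after tango exposure. If tango works as assumed, this biases the tango-versus-control follow-up contrast toward no difference; that direction does not depend on the numerical assumptions. It would hide a benefit at follow-up and would not create one.

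The size cannot be derived from the documents, which give no crossover share, start date or dose-response. Under the stated assumptions the loss in pairwise follow-up power runs from slight, if few controls cross over, to about half, if all do. The interaction test loses less, and how much depends on r.

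A reader might take this as undermining the primary analysis as a whole. It does not: one cell of nine is at risk, and the comparisons in step 6 are largely intact.

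**What to change.** Reword the sentence in section 5 (Behavioral Control Condition) so that BC participants may join an IG or EG class only after their 1-month follow-up evaluation is complete, and say that the later class has no study evaluations. This also protects the 1-week visit and removes the ambiguity about evaluations. It leaves the randomised interventions and the planned analysis unchanged. If staff already work in this order, it only records the practice.

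The cost is one sentence, and the optional class starts up to about one month later for controls who want it.

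A separate rule for controls who start early anyway is optional. Setting aside their BBS values after class start while keeping pre and post is a choice of estimand that would need justifying. It would also need a mixed model that accepts incomplete cases, because the planned RM ANOVA in its conventional form would drop those participants.
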